4. PARTICIPANT DISPOSITION

4.1. Participant Enrollment and Disposition

A summary of participant enrollment will be provided by treatment group and total for each country, investigator within a country, and overall. For each column, the denominator for the percentage calculation will be the total number of participants analyzed for that column.

A summary of participant disposition will be provided by treatment group and total based on all screened participants. This summary will present the number of participants screened, the number of participants who did not meet eligibility criteria and were not randomized, the number of participants who met all eligibility criteria but were not randomized with reasons participants not randomized, the number of participants randomized but never dosed (if applicable), number of participants in the Safety Analysis Set and the number of participants in each of the following categories as applicable:

- Completed study drug
- Did not complete study drug with reasons for premature discontinuation of study drug
- Completed study
- Did not complete the study with reasons for premature discontinuation of study

For summary, participants with study drug premature discontinuation are defined as participants who answered “No” to “Did subject complete study drug dosing as specified per protocol?” and had a discontinuation reason other than “Investigator Discretion” (with comment of “Due to Clinical hold”) in Study Drug Completion eCRF).

Participants who prematurely discontinued study are defined as participants who answered “No” to “Did the subject complete the protocol-planned duration of the study?” in Study Completion eCRF)

For the status of study drug and study completion and reasons for premature discontinuation, the number and percentage of participants in each category will be provided. The denominator for the percentage calculation will be the total number of participants in the Safety Analysis Set corresponding to that column. In addition, a flowchart will be provided to depict the disposition.

The following by-participant listings will be provided by participant ID number in ascending order to support the above summary tables:

- Reasons for premature study drug or study discontinuation

4.2. Extent of Study Drug Exposure and Administration

Study drug administration and study drug dispensing information will be collected in the Study Drug Administration and Study Drug Accountability eCRFs. Extent of exposure to study drug will be examined by assessing the total duration of exposure to study drug and the level of adherence relative to the study drug if applicable.

4.2.1. Duration of Exposure to Study Drug

Duration of exposure to study drug will be summarized. Due to long acting feature of study drug, duration of follow-up to study drug will consider the prolonged exposure of LA study drug (ie, SC LEN, GS-5423, GS-2872) after the last dose date of study drug through the ART restart date or the end of study, respectively.

For long acting regimen period analysis, last exposure date of LA regimen is defined in Section 3.8.1 for participants who prematurely discontinued study drug or completed study drug.

Duration of study drug exposure will be defined as (the last exposure date – the first dose date + 1), and duration of exposure will be expressed in weeks using up to 1 decimal place (eg. 4.5 weeks).

Duration of exposure will be summarized using descriptive statistics (n, mean, SD, median, Q1, Q3, minimum, and maximum) and as the number and percentage of participants exposed and remained through the following time periods: 1 day, 2 days, 4 weeks (28 days), 8 weeks (56 days), 16 weeks (112 days), 24 weeks (168 days), 26 weeks (182 days), 30 weeks (210 days), 34 weeks (238 days), 38 weeks (266 days), 42 weeks (294 days), 54 weeks (378 days), etc. Summaries will be provided based on the Safety Analysis Set for LA Regimen Period (up to 26 weeks) and for Whole Study Period separately (up to 54 weeks). No inferential statistics will be provided.

4.2.2. Study Drug Administration

Study drug administration for participants in the Primary Cohort and in the optional Pilot Cohort will be summarized by treatment groups for the following items:

- Number and percentage of participants who received oral LEN on Day 1 and Day 2, respectively
- Number and percentage of participants who received LEN SC injection on Day 1
- Number and percentage of participants who received IV infusion of GS-5423 on Day 1
- Number and percentage of participants who received IV infusion of GS-2872 on Day 1.

4.3. Protocol Deviations

Participants who did not meet the eligibility criteria for study entry, but enrolled in the study will be summarized. The summary will present the number and percentage of participants who did not meet at least 1 eligibility criterion and the number of participants who did not meet specific criteria based on the Safety Analysis Set. A by-participant listing will be provided for those participants who did not meet at least 1 eligibility (inclusion or exclusion) criterion.

Protocol deviations occurring after participants entered the study are documented during routine monitoring. The number and percentage of participants with important protocol deviations and number of important protocol deviations by deviation category (eg, eligibility criteria, informed consent) will be summarized by treatment group and total for the Safety Analysis Set. A by-participant listing will be provided for those participants with important protocol deviation.

4.4. Assessment of COVID-19 Impact

This study was ongoing during the novel coronavirus (COVID-19) pandemic which has an impact on the study conduct. Some participants were unable to attend onsite visits due to shelter in place guidelines, site closures, or other reasons. This section describes how special situations due to COVID-19 will be handled in the analysis.

4.4.1. Study Drug or Study Discontinuation Due to COVID-19

A by-participant listing of reasons for premature study drug or study discontinuation due to COVID-19 will be provided if applicable.

4.4.2. Protocol Deviations Due to COVID-19

A by-participant listing will be provided for participants with important protocol deviations related to COVID-19 if applicable. A separate listing will be provided for participants with non-important protocol deviations related to COVID-19 if applicable.

4.4.3. Missed and Virtual Visits Due to COVID-19

A by-participant listing of participants with missed or virtual visits due to COVID-19 will be provided by participant ID number in ascending order.

Information regarding missed or virtual visits due to COVID-19 will be collected as free text in the CRF comment fields. The determination of missed or virtual visits due to COVID-19 will be done using Natural Language Processing (NLP) to search the CRF comment fields. A detailed explanation of the algorithm is given in [Appendix 4](#).

4.4.4. Adverse Events Due to COVID-19

AEs of COVID-19 will be included in analyses of AEs if applicable, which will be determined through COVID-19 SMQ Narrow search. A by-subject listing of AEs of COVID-19 will be provided if applicable.

4.4.5. Overall Assessment of COVID-19 Pandemic Impact

For subjects affected by COVID-19 infection and/or pandemic while participating in the study, a listing of the following individual COVID-19 related outcome categories will be provided:

- Death due to COVID-19
- Adverse event of COVID-19, as determined by COVID-19 SMQ narrow search
- Specific adverse event directly associated with the pathogen causing COVID-19, as determined by Medical Surveillance Team (MST)
- Hospitalization (using data from AE eCRF) due to adverse event of COVID-19 as defined above
- Tested positive for COVID-19
- Study drug discontinuation due to COVID-19
- Study discontinuation due to COVID-19
- Missed visits due to COVID-19
- Missed key assessments due to COVID-19, with Key assessments include the assessments contributing to primary and key secondary endpoints, including follows:
 - Missing reporting of any new treatment-emergent AE through Week 26 visit, or any update of existing treatment-emergent AE during the same period of time, could be further evaluated for missing key assessment
 - Missing HIV-1 RNA at Week 26 visit

In addition, composite broad COVID-19 impact indicator will be derived based on the following individual categories defined above: death, adverse event, hospitalization, tested positive, study drug discontinuation, study discontinuation, missed visits, and missed key assessments. Composite specific COVID-19 impact indicator will be derived based on death, specific adverse event, and tested positive.

5. BASELINE CHARACTERISTICS

5.1. Demographics and Baseline Characteristics

Participant demographic variables (ie, age, sex at birth, gender identity, sexual orientation, race, and ethnicity) and baseline characteristics (body weight [in kg], height [in cm], body mass index [BMI; in kg/m²]) will be summarized by treatment group and overall using descriptive statistics for continuous variables and using number and percentage of participants for categorical variables. The summary of demographic data will be provided for the Safety Analysis Set.

A by-participant demographic and baseline characteristic listing, including the informed consent date, will be provided by participant ID number in ascending order.

5.2. Other Baseline Characteristics

The following baseline disease characteristics will be summarized by treatment group and overall using descriptive statistics for participants in the Safety Analysis Set:

- HIV-1 RNA categories (copies/mL): (a) < 50, (b) ≥ 50
- CD4 cell counts (/uL)
- CD4 cell counts categories (/uL): (a) < 50, (b) ≥ 50 to < 200, (c) ≥ 200 to < 350, (d) ≥ 350 to < 500, and (e) ≥ 500
- CD4 percentage (%)
- Mode of infection (HIV risk factors)
- HIV disease status
- eGFR_{CG} (mL/min)
- Duration of baseline ARV medication

A by-participant listing of other baseline characteristics will be provided by participant ID number in ascending order.

5.3. Medical History

Medical history will be collected at screening. Medical history data will be coded and listed.

6. EFFICACY ANALYSES

Secondary endpoints of this study include efficacy endpoints as described below. For efficacy analyses (except for FDA-defined snapshot endpoints), two sets of analyses will be conducted unless otherwise specified: LA Regimen Period analysis and Whole Study Period analysis.

6.1. Secondary Efficacy Endpoints

6.1.1. Definition of the Secondary Efficacy Endpoints

The secondary efficacy endpoints of this study are:

- Proportion of participants with HIV-1 RNA ≥ 50 copies/mL at Weeks 26 as defined by the FDA-defined snapshot algorithm
- Proportion of participants with HIV-1 RNA < 50 copies/mL at Weeks 26 as defined by the FDA-defined snapshot algorithm
- Change from baseline in CD4+ cell counts at Weeks 26.

6.1.2. FDA-defined Snapshot Algorithm

The analysis window at Week 26 is defined as from Study Day 176 to Study Day 224, inclusive. All HIV-1 RNA data collected on-treatment (ie, data collected up to the earliest date of (196 days [28 weeks] after the dose date of complete long acting regimen, date of restarting ART) will be used in the US FDA-defined snapshot algorithm {[U. S. Department of Health and Human Services 2015](#)}. Virologic outcome will be defined as the following categories:

- HIV-1 RNA < 50 copies/mL: this includes participants who have the last available on-treatment HIV-1 RNA < 50 copies/mL in the Week 26 analysis window
- HIV-1 RNA ≥ 50 copies/mL: this includes participants
 - a) Who have the last available on-treatment HIV-1 RNA ≥ 50 copies/mL in the Week 26 analysis window, or
 - b) Who do not have on-treatment HIV-1 RNA data in the Week 26 analysis window and
 - i) discontinue study drug prior to or in the Week 26 analysis window due to lack of efficacy, or
 - ii) discontinue study drug prior to or in the Week 26 analysis window due to AE or death and have the last available on-treatment HIV-1 RNA ≥ 50 copies/mL, or
 - iii) discontinue study drug prior to or in the Week 26 analysis window due to reasons other than AE, death, or lack of efficacy and have the last available on-treatment HIV-1 RNA ≥ 50 copies/mL.

- No Virologic Data in the Week 26 Window: this includes participants who do not have on-treatment HIV-1 RNA data in the Week 26 analysis window because of the following:
 - a) Discontinuation of study drug prior to or in the Week 26 analysis window due to AE or death and the last available on-treatment HIV-1 RNA < 50 copies/mL, or
 - b) Discontinuation of study drug prior to or in the Week 26 analysis window due to reasons other than AE, death, or lack of efficacy and the last available on-treatment HIV-1 RNA < 50 copies/mL or,
 - c) Missing data during the window but on study drug.

The flowchart of the US FDA-defined snapshot algorithm is provided in [Appendix 2](#).

The Week 26 virologic outcomes for the US FDA-defined snapshot algorithm will be flagged in the listings.

Note, for switch trials, the US FDA-defined snapshot algorithm classifies participants who discontinue study drug due to AE or death and have the last available on-treatment HIV-1 RNA value ≥ 50 copies/mL in the “HIV-1 RNA ≥ 50 copies/mL” category. For treatment naïve study population, these participants will be classified in the “No Virologic Data in the Week 26 Window” category.

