6.8.2. Virologic Failure

Participants who meet the criteria listed below will be considered to have VF:

- Participants with HIV-1 RNA ≥ 200 copies/mL on 2 consecutive visits will be considered to have VF. The blood sample from the confirmation visit will be the primary sample used for HIV-1 genotypic and phenotypic testing of capsid and env for study drugs (LEN, GS-5423, and GS-2872) and genotypic testing of RT, PI, and/or IN genes for the baseline ART regimen. Samples collected at baseline will be used for comparison of genotypic and phenotypic testing of study drugs at VF. The participant will be restarted on their baseline ART regimen (or compatible regimen selected by the investigator) and continue on study follow-up but will not receive additional doses of the study regimen. Participants will return for an unscheduled visit, 4 weeks after restarting their baseline ART regimen (or compatible regimen selected by the investigator) to confirm virologic suppression.
- Participants with HIV-1 RNA ≥ 200 copies/mL at study discontinuation or Week 26 will be considered to have VF. The blood sample from the last visit or Week 26 with HIV-1 RNA ≥ 200 (ie, not confirmable) will be the primary sample used for HIV-1 genotypic and phenotypic testing. The participant will be restarted on their baseline ART regimen (or compatible regimen selected by the investigator) and continue on study follow-up but will not receive additional doses of the study regimen. Participants will return for a unscheduled visit 4 weeks after restarting their baseline ART regimen (or compatible regimen selected by the investigator) to confirm virologic suppression.
- Participants with ongoing HIV-1 RNA ≥ 50 copies/mL but who do not meet criteria for VF must be discussed with the medical monitor.

For participants who are off study drug but remain on study, it will be the investigator's discretion to manage VR.

Figure 6-1. Virologic Rebound Schema

VF = virologic failure

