8.10. Sample Size

Although the sample size in this study is determined based on practical considerations and past experience with similar types of studies, assuming the 2 treatment groups have a similar virologic suppression rate, a total of 20 participants in the Primary Cohort will provide at least 35% power to show the lower bound of 95% CI for Week 26 virologic response rate (HIV-1 RNA < 50 copies/mL as defined by the FDA-defined snapshot algorithm) is greater than 83%. It was assumed that the virologic response rate at Week 26 was 95% (based on Gilead studies GS-US-380-1844 and GS-US-380-4030), 12% was a clinically tolerable margin for Phase 1b studies, and a one-sided exact test with a significance level 0.025 was used. The sample size and power calculations were made using the statistical software package PASS (Version 14, NCSS, LLC; Kaysville, Utah, USA).

The estimated 95% CI for possible range of VF rate is provided in [Table 8-1](#). For example, with 1 VF event occurrence (5% estimated VF rate), a sample size of 20 participants can provide 95% confidence that the true VF rate is unlikely to be higher than 24.9%.

Table 8-1. Estimated Virologic Failure Rate and its 95% CIs (from the Clopper-Pearson Exact CI) Based on Number of Virologic Failure Event in Each Group or in Total

Sample Size	20				
Number of VF Events	0	1	2	3	4
Estimate of Incidence of VF (%)	0.0	5.0	10.0	15.0	20.0
Lower Bound of 95% CI (%)	0.0	0.1	1.2	3.2	5.7
Upper Bound of 95% CI (%)	16.8	24.9	31.7	37.9	43.7

VF = virologic failure

Software: SAS® Version 9.4. (SAS Institute Inc., Cary, NC, USA)

A total of approximately 20 participants in the Primary Cohort will provide reasonable assessment of safety and the descriptive PK profile throughout the study. A total of up to 20 participants in the optional Pilot Cohort is based on practical considerations.

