3.1.3. Per Protocol Analysis Set

The **Per Protocol (PP) Analysis Set** includes all participants in the FAS excluding participants meeting any of the following criteria:

- Did not have on-treatment HIV-1 RNA in the Week 26 analysis window, except when missing is due to discontinuation of study drug for lack of efficacy as in [Table 3-1](#). (Note: lack of efficacy is defined as having the check-box for Lack of Efficacy marked as the reason for premature study drug discontinuation on the study drug completion eCRF page.)
- Received partial or missed doses on Day 1 or Day 2.
- Prior receipt of any anti-HIV-1 mAbs (including ibalizumab).
- Have been treated with immunosuppressant therapies or chemotherapeutic agents (eg, corticosteroids, immunoglobulins, and other immune- or cytokine-based therapies) within 4 weeks of study screening or have an anticipated need for such treatment during the study.

Table 3-1. Participants Excluded from Per Protocol Analysis Set Due to Premature Discontinuation of Study Drug and/or Missing HIV-1 RNA Assessment in Week 26 Analysis Window

Discontinuation from Study Drug prior to or on the Upper Bound of Week 26 Analysis Window		HIV-1 RNA Data on Treatment Available in Week 26 Analysis Window	
		Yes	No
Yes	Due to Lack of Efficacy	+	+
	Due to Other Reasons	+	-
No		+	-

+ = Inclusion of Participants in Week 26 PP analysis set; - = Exclusion of Participants in Week 26 PP analysis set.
On-Treatment HIV-1 RNA data include all HIV-1 RNA data collected up to the earliest date of (196 days [28 weeks] after the dose date of complete long acting regimen, date of restarting ART).

The date of study drug premature discontinuation is the last exposure date for participants who prematurely discontinued study drug.

For the Per Protocol analysis, efficacy data up to the earliest date of (196 days [28 weeks] after the dose date of complete long acting regimen, date of restarting ART) will be included.

The Per Protocol Analysis Set is the secondary analysis set for efficacy analysis.

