3.8.1. Definition of Key Dates and Study Day

Study Day 1 is defined as the day when the first dose of any study drug was taken, as recorded on the Study Drug Administration eCRF (ie, oral LEN, SC LEN or infusion drugs [GS-5423, GS-2872]).

Last Dose Date is defined as the latest dose date of any study drug as recorded on the Study Drug Administration eCRF (ie, oral LEN, SC LEN or infusion drugs (GS-5423, GS-2872) for participants who prematurely discontinued study drug or completed study drug according to Study Drug Completion eCRF.

Study Days are calculated relative to Study Day 1 of study drug and derived as follows:

- For postdose study days: Assessment Date – First Dose Date + 1
- For days prior to the first dose: Assessment Date – First Dose Date

Baseline Value is defined as the last value obtained on or prior to the first dose of study drug.

Last Study Date is the latest clinic visit dates, and/or the laboratory visit dates, whichever is latest, including the any follow-up visit dates, for participants who prematurely discontinued study or completed study according to the Study Completion eCRF.

Last Exposure Date is defined as follows for participants who prematurely discontinued study or complete study according to Study Completion eCRF (i.e. participant answered “No” or “Yes” for “Did the participant complete the protocol-planned duration of the study” on Study Completion form):

- For participants who receive any injection or infusion, last exposure date is defined as last study date.
- For participants who do not receive any injection or infusion (i.e. for those who only receive oral LEN), last exposure date is defined as the earliest of the last dose date plus 60 days and the last study date.

The last exposure date is defined considering the prolonged exposure of LEN, GS-5423, and GS-2872 after the last dose date of LEN, GS-5423, and GS-2872 through the end of study.

Last Exposure Date of LA Regimen is defined as follows for participants who prematurely discontinued study drug or complete study drug according to Study Drug Completion eCRF (i.e. participant answered “No” or “Yes” for “Did participant complete study drug dosing as specified per protocol” on Study Drug Completion form):

- the earliest date of last study day or ART restart day for participants who prematurely discontinued study or complete study, or

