Appendix 2. Flowchart of US FDA-defined Snapshot Algorithm (for Long Acting Switch Trial)

The following flowchart for US FDA-defined snapshot algorithm is based on the US FDA Guidance on Human Immunodeficiency Virus-1 Infection: Developing Antiretroviral Drugs for treatment {U. S. Department of Health and Human Services 2015}.

*On-Treatment HIV-1 RNA data include all HIV-1 RNA data collected up to the earliest date of (196 days [28 weeks] after the dose date of complete long acting regimen, date of restarting ART).

The dose date of complete long acting regimen refers to the date of dosing with complete long acting drugs (GS-5423, GS-2872, and SC LEN) (ie, Day 1).

Participants with study drug premature discontinuation are defined as participants who were answered “No” to “Did subject complete study drug dosing as specified per protocol?” and had a discontinuation reason other than “Investigator Discretion” (with comment of “Due to Clinical hold”) in Study Drug Completion eCRF).

The date of study drug premature discontinuation is the last exposure date of LA regimen for participants who prematurely discontinued study drug.

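### The Per Protocol set dates discontinuation so that an early virologic failure can be excluded even when marked Lack of Efficacy, and the snapshot may class the same failure as no data, depending on one eCRF answer

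*SAP*

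**What the plan says.** **Management of failure.** Under Protocol 6.8.2 a participant with virologic failure (VF) "will be restarted on their baseline ART regimen (or compatible regimen selected by the investigator) and continue on study follow-up". The participant leaves the regimen but stays in the study.

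**On-treatment data.** SAP 6.1.2 ends on-treatment HIV-1 RNA at ART restart or 196 days after dosing, whichever is earlier. The Week 26 window is Day 176 to 224.

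**Snapshot without a window value.** Rules b(i) to b(iii) of SAP 6.1.2 class the participant as >= 50 copies/mL, but each requires that study drug was discontinued. For a participant not recorded as discontinued, the remaining rule is (c), "Missing data during the window but on study drug", which means No Virologic Data.

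**Who counts as discontinued.** SAP Appendix 2: "Participants with study drug premature discontinuation are defined as participants who were answered" No to a question about completing dosing per protocol (with a carve-out for a clinical hold). SAP 4.1 uses the same definition. Neither mentions VF or ART restart.

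**When discontinuation is dated.** Two different dates are used:
- SAP 3.1.3, under Table 3-1: "The date of study drug premature discontinuation is the last exposure date for participants who prematurely discontinued study drug".
- SAP Appendix 2: "The date of study drug premature discontinuation is the last exposure date of LA regimen for participants who prematurely discontinued study drug".

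SAP 3.8.1 separates them. On the first: "For participants who receive any injection or infusion, last exposure date is defined as last study date". The second ends at ART restart or the last study day, whichever comes first.

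**Per Protocol exception.** The first bullet of SAP 3.1.3 keeps participants whose missing window value is due to discontinuation for lack of efficacy, as shown by an eCRF check-box.

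**The concern.** The >= 50 copies/mL proportion is a named secondary endpoint, and it is there to count failures. A failure managed as the protocol directs restarts ART, and so loses the on-treatment value that would have classed it directly. Its classification then rests on whether and when the participant is held to have discontinued a regimen whose dosing is complete by Day 2.

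Two things can go wrong. In the Per Protocol set, the date in 3.1.3 can move the discontinuation to the end of follow-up, outside the range that Table 3-1 looks at. In the snapshot, a participant who received every dose may not be recorded as discontinued at all. With about 20 participants per cohort, one lost failure is visible in the estimate. The final analysis also covers the Pilot Cohort, whose participants were sensitive to only one antibody.

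**Working it through.** **1. The plan's own figures.** Protocol 8.10 states that "a total of 20 participants in the Primary Cohort will provide at least 35% power", with a true rate of 95%, a null rate of 83% and a one-sided exact test at 0.025.
- Requiring 20/20: type I error = 0.83^20 = 0.0241, which is allowed. Requiring 19/20 gives 0.1227, which is not.
- Power = 0.95^20 = 0.3585. The stated 35% reproduces.
- Clopper-Pearson for 0/n has upper limit 1 - 0.025^(1/n). For n = 20 this is 16.8%. For 1/20 the interval is 0.1 to 24.9%. Both match Protocol Table 8-1, as do the rows for 2 to 4 events.

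**2. Which failures are at issue.** Treatment visits have a window of +/- 3 days, and the retest comes 14 to 21 days later.
- A first value >= 200 at Week 20 is confirmed by Day 140 + 3 + 21 = 164 at the latest. First rises at Weeks 4 to 16 are confirmed earlier. All precede Day 176.
- A first rise at Week 24 is confirmed between Day 168 - 3 + 14 = 179 and Day 168 + 3 + 21 = 192. That is normally inside the window and on treatment, so rule (a) counts it directly.

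The issue is therefore limited to failures that restart ART with no on-treatment value in Day 176 to 224.

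**3. Per Protocol trace, with Lack of Efficacy ticked.**
- The participant was injected and infused, so the last exposure date is the last study date.
- Anyone who attends Week 38 is seen no earlier than Day 266 - 3 = 263, which is after Day 224.
- By the 3.1.3 date, discontinuation is then not on or before the upper bound of the window. Table 3-1 gives row No, no on-treatment RNA: excluded.
- By the Appendix 2 date, discontinuation falls at ART restart. Table 3-1 gives row Lack of Efficacy: included.

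The same participant is excluded or included according to which of the SAP's two dates is programmed.

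**4. Snapshot trace.**
- Dosing question No, reason Lack of Efficacy: Appendix 2 dates discontinuation at ART restart, and rule b(i) gives >= 50.
- Dosing question No, another reason, last on-treatment RNA >= 50: rule b(ii) or b(iii) gives >= 50.
- Dosing question Yes: only rule (c) is left, so No Virologic Data. Table 3-1 then also excludes the participant from the Per Protocol set.

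**5. Size.** The documents give no count of early failures, so k is an assumption. The table takes a Primary Cohort of 20 with everyone else suppressed and in the Per Protocol (PP) set. Entries are % (95% Clopper-Pearson).

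| k | >= 50, counted (FAS) | >= 50, misrouted (FAS) | >= 50, PP if excluded | < 50, FAS either way | < 50, PP if excluded |
|---|---|---|---|---|---|
| 1 | 5.0 (0.1-24.9) | 0 (0-16.8) | 0/19 (0-17.6) | 95.0 (75.1-99.9) | 19/19 = 100 (82.4-100) |
| 2 | 10.0 (1.2-31.7) | 0 (0-16.8) | 0/18 (0-18.5) | 90.0 (68.3-98.8) | 18/18 = 100 (81.5-100) |
| 3 | 15.0 (3.2-37.9) | 0 (0-16.8) | 0/17 (0-19.5) | 85.0 (62.1-96.8) | 17/17 = 100 (80.5-100) |
| 4 | 20.0 (5.7-43.7) | 0 (0-16.8) | 0/16 (0-20.6) | 80.0 (56.3-94.3) | 16/16 = 100 (79.4-100) |

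For one failure in an arm of 10, the FAS >= 50 rate is 10.0% (0.3 to 44.5) if counted and 0% (0 to 30.8) if misrouted.

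**The case against.** A reader might infer that every early failure is lost from the snapshot. The documents do not support that. Rules b(i) to b(iii) exist to catch such cases, and they work once premature discontinuation is recorded. That recording is plausible: Protocol 3.4 puts treatment at about 26 weeks, Protocol 6.6 lists VF among the grounds for discontinuing study drug, and the completion form carries a Lack of Efficacy box, which would make little sense if dosing to Day 2 were all it asked about. What stands against this is that the SAP defines discontinuation only through the dosing question and does not say how it is answered for someone fully dosed. Two sites could record identical failures differently.

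A reader might also infer that efficacy as a whole is overstated. It is not. No Virologic Data is already a non-response, so the FAS < 50 rate does not move.

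On the Per Protocol set, it can be said that the bullet's express exception should override the footnote. That is a fair reading of intent, but then the section contradicts itself, and a program that follows the footnote date removes the failure. The set is also only supportive.

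Missing = Failure (SAP 6.2.2.1) is a partial backstop: it treats these cases as failures but tabulates them as missing. Flagged listings would let individual cases be checked, but they do not correct the tabulated rate.

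**Conclusion.** The Per Protocol date is wrong as written, with high confidence. It conflicts with the exception in the same section and with Appendix 2. A failure with no on-treatment value in the window who is followed past Day 224 is excluded even when marked Lack of Efficacy. One such case in 20 moves Per Protocol < 50 from 95% to 100%. This does not depend on how the dosing question is answered.

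The snapshot gap is real but conditional, with medium confidence. It opens only if that question is answered Yes, and then one failure in 20 moves the FAS >= 50 rate from 5.0% to 0%. The eCRF and its completion guidelines are not among the documents, and the Appendix 2 flowchart is not shown, so neither could be checked.

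The FAS < 50 rate, the 35% power and the primary endpoint (treatment-emergent SAEs) are unaffected. This should be corrected before database lock, but it does not put the main conclusions at risk.

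**What to change.** 1. In SAP 3.1.3, replace the last exposure date with the last exposure date of LA regimen, to match Appendix 2.
2. In SAP 6.1.2, Table 3-1 and Appendix 2, state that ART restart before any on-treatment sample in the Week 26 window counts as premature discontinuation on the restart date, whatever the dosing-completion answer.
3. Class such a participant as >= 50 copies/mL, and keep the participant in the Per Protocol set, if protocol VF criteria were met or the last on-treatment HIV-1 RNA was >= 50. Otherwise class as No Virologic Data.

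The cost is one changed phrase and a small derivation from the ART restart date, which SAP 3.8.1 already defines. No new data are needed. The reported failure rate may become less favourable. The change should precede database lock, which is also the deadline that SAP 6.1.3.1 sets for deciding Per Protocol exclusions.
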